1.6 The Multi-frequency Bioimpedance in the Early Detection of Lymphoedema Trial

We will assess multi-frequency bioimpedance monitoring compared to perometer arm measurements in women after axillary node clearance (ANC) in 9 centres for the first 1100 patients enrolled in the 5 year study. We will use bioimpedance monitoring during the study to determine its value in predicting response to compression garment therapy. Within the study we will assess reproducibility of both methods across centres and robustly establish both intra and interobserver error rates for both methods in the study population. Subsequent recruits, as part of the 9 month study, will not undergo this as enough data will be gathered from the original cohort.

All women undergoing ANC in the UHSM Breast Unit have been invited to have preoperative 1,3,6,12 and 18 monthly bilateral arm measurements with a perometer (Pero-Systems 350S) and circumferential arm tape measurements. Of the last 270 women approached undergoing ANC within the last 11 months, 183 (67%) agreed to participate. We will use 9 centres who will monitor women undergoing ANC from pre-surgery baseline with perometer measurements and BEA to compare the sensitivity and specificity of both techniques for predicting chronic lymphoedema development. Identifying the most sensitive and specific method for detecting chronic lymphoedema would enhance selection of patients for intervention with arm sleeves should the intervention prove cost effective. Please note, this assessment will only be carried out in the initial 1100 recruits, as part of the 5 year study.

We have negotiated agreement with the manufacturers for provision and training in the use of L-DEX U400 bioimpedance spectroscopy devices for all centres taking part in the 5 year study with the appropriate software and electrodes to carry out a health technology assessment.

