2.0 TRIAL DESIGN

1100 women undergoing ANC for breast cancer in 9 centres across the UK will be approached to undergo baseline (pre-operative) and subsequent BEA monitoring, along with perometer arm measurements (see flow diagram). A comparison of the sensitivity and specificity of BEA versus perometer measurement will be made firstly in women who develop arm swelling >10% by 6 months (estimated at 231/1100 (21%) of the initial group). Percentages are estimated from ALMANAC Trial (see Annex 4d). Secondly women with an arm volume increase 4-8.9% at 1, 3, 6 months where effectively the BEA 6 months readings will be compared with final 18 month perometer scores to assess the prediction of lymphoedema at 18 months by BEA. Thirdly, women with a <4% Perometer arm volume increase up to 6 months (estimated n=363/1100 with estimated lymphoedema at 18 months of 46 (14% of 264)) will be used to determine the sensitivity and

specificity of BEA 6 month measures compared to the perometer 6 month measurement in predicting the 18 month outcome.

We originally estimated we would need to screen over 1000 patients to enrol sufficient women into the PLACE Trial using perometer measurements, we will determine if BEA has a >80% sensitive and a >80% specific accuracy and currently the specificity of arm swelling measured by perometer is 87% specific for subsequent lymphoedema at 18 months with a sensitivity of 54% (assessed from ALMANAC trial data). We will recruit 1100 women before ANC into the five year study to allow for 10% drop-out over the course of the study.

The Perometer sensitivity is reported as 85% +/-3.6% (95% CI 81.4% to 88.6%) and we will be able to detect a greater or equal to 7% improvement in sensitivity with BEA to 92+/-2.5% (95%CI: 89.5-94.5%) and the Perometer specificity is 55% +1-4.1% (95% CI 50.9% to 59.1%) thus we will be able to detect a >9% improvement in specificity with BEA to 64%+/-3.9% (95%CI:60.1 to 67.9%) with this sample size, since the confidence intervals do not overlap.

Gold standard at 18 months	Test P+	Test P-	Total
	+168[contact]
	-168[contact]
Total	336[contact]

sensitivity = 307/352 = 87%
 specificity = 284/523 = 54%

Arm volume measurement at 1 month will not be used to implement treatment outside of the trial. In women who develop lymphoedema >10% at 3 months, sleeves will be applied and the 3 month BEA value compared to the perometer used in the analysis. For all others, the 6 month value will be used.

[figure not shown]

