5 STATISTICAL ANALYSIS

Analysis 1 and 2 will directly compare BEA and perometer assessment at a given time point (6 and 18 months). The reported concordance/correlation in small series is 0.93¹³⁴¹. Thus, even if a sleeve has been applied in patients before 6 months' measurements and the arm circumference has been reduced, the reduction in fluid in the arm should have reduced both the perometer and BEA scores concomitantly.

Sample Size Calculation

We estimate 1100 women are needed for screening by perometer to recruit 270 women to the PLACE trial and this sample size of 1100 (derived from having approached 1500 women to take part in the study) allows us to assess equivalence for sensitivity and specificity for BEA compared to perometer measurement with tight confidence intervals. Previous reported correlation between the techniques is very high¹¹⁵, and this sample size allows us to have a 95% Confidence Interval (CI) around our sensitivity and specificity estimates such that they are $\pm 5\%$ or less. Thus if perometer and BEA are equivalent in sensitivity and specificity to within 5% of each other, we would expect that the BEA would become the preferred option as it would be mobile, non-invasive and simpler to use in any outpatient setting compared to a fixed, large instrument, such as the perometer. There will be less patients with lymphoedema at 6 months but nonetheless if BEA sensitivity is 95% of the perometer sensitivity, we can demonstrate this with a 95% CI of 91.42% to 97.49%. If the BEA sensitivity rate was as low as 90%, we would have a 95% CI of 85.12% to 93.49%. All subsequent analyses will use sample sizes based on larger numbers as there will be more lymphoedema events at 18 months and again at 36 months but their confidence intervals are within $\pm 5\%$. We have used the exact method for calculating confidence intervals for a binomial proportion (Documenta Geigy Scientific tables page 185 equation 769); the actual calculation was done using the www.measuringusability.com/wald.htm website calculator.

The sample will allow us to measure accurately, inter- and intra-technique variability at different time points.

Analyses 1 to 3 will assess whether BEA can be used instead of perometer in defining lymphoedema status. The second group of analyses is to look for any variables collected at operation or in the first 6 months post operation that singly or in combination can be used to predict lymphoedema status at or beyond 18 months.

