A further assessment of the BEA value cut off level will be made to see if a change in the standard definition is worth recommending (ROC analysis). This will be done at 18m from the start of the study (using cases accrued in the first year) and repeated on the new cases post 1 year recruitment to see if a new cut off level works on the second data group. The final sensitivity and specificity analysis will take place 6 months after the last case is recruited.

Analysis 2: Analysis of the sensitivity and specificity of the 18 month BEA assessment status (lymphoedema or not) against the 'gold standard' 18 month perometer assessment status (lymphoedema or not) using all data available at 18 months.

This analysis uses all the data available at 18 months, following the same logic and procedures as Analysis 1. Assuming at least 1,000 women are followed-up to 18 months after surgery, there will be more lymphoedema cases, this is estimated to be 35% of the total group (i.e. 350 cases). The sensitivity calculations produce a 95% CI for a 95% BEA sensitivity rate (333/350) against the perometer status at 18 months of 92.34 to 97.15 (again using the 'exact' method). The other 650 cases are used for the specificity calculation, here the 95% CI for 95% BEA specificity (618/650) has a 95% CI of 93.12 to 96.61. Consequently if sensitivity is <92% or specificity is <93% we can conclude that the true BEA rates are not as high as 95%.

Analysis 3: Assessment of the relationship between perometer measurement and BEA measurement. Any changes will be measured by both systems at different time points (1m, 3m, 6m, 12m and 18m and later on out to 5 years) and all results will be used as the modelling will be based on the paired perometer and BEA values. This will be used to define the relationship between the two methods (we will use Bland-Altman methods^{136,371} at individual time points and generalized estimating equations (GEE) regression models across time points). The relationship established may lead to a clearer definition of 'true' lymphoedema status when using either system.

Analysis 4: Cox regression multivariate analysis of the time to Lymphoedema (as defined by perometer) to find out what combination of variables gives the best prediction of these events.

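### Section 2.0: the two sensitivity half-widths imply different numbers of cases (378 and 452), and ±2.5 points for BEA is narrower than any case count planned in the protocol supports

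*Protocol*

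**What the plan says.** Section 2.0 of the protocol sets out what the sample of 1100 can show. For the perometer it states: "The Perometer sensitivity is reported as 85% +/-3.6% (95% CI 81.4% to 88.6". For BEA it projects "92+/-2.5% (95%CI: 89.5-94.5". The specificities are treated in the same way: 55% ±4.1 for the perometer ("95% CI 50.9% to 59.1") and, for BEA, "64%+/-3.9% (95%CI:60.1 to 67.9%) with this sample size, since the confidence intervals do not overlap". Separation of the intervals is the only reason section 2.0 gives for calling these differences detectable.

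The comparison is within patients. Section 1.6 says the centres will "monitor women undergoing ANC from pre-surgery baseline with perometer measurements and BEA to compare the sensitivity and specificity of both techniques".

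The protocol gives two case counts for 18 months. Analysis 2 in section 5 assumes 1000 women followed and says of the lymphoedema cases that "this is estimated to be 35% of the total group (i.e. 350 cases", which leaves 650 non-cases. The table in section 2.0, headed as an 18-month gold standard, gives "sensitivity = 307/352 = 87"%, with 523 as the specificity denominator.

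**The concern.** If both devices are applied to the same women, the two sensitivities are proportions of the same group, namely those who have lymphoedema by the reference standard. A half-width then depends only on the proportion and on that one count. The two printed half-widths do not appear to come from one count, and the BEA figure looks too small for the number of cases the protocol expects.

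At stake is the margin behind the 7-point claim. The printed intervals are 0.9 points apart (88.6 against 89.5). If the BEA interval is too narrow, that margin is overstated.

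**Working it through.** **Inputs.** Section 2.0: sensitivities 85% ±3.6 and 92% ±2.5; specificities 55% ±4.1 and 64% ±3.9. The level is 95% (section 5, sample size: "this sample size allows us to have a 95% Confidence Interval (CI) around our sensitivity and specificity estimates"), so z = 1.96. Analysis 2: 350 cases and 650 non-cases. Section 2.0 table: 352 and 523.

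**Formula.** The printed intervals are symmetric, so the normal approximation is the natural reading: h = z·√(p(1−p)/n), which gives n = z²·p(1−p)/h².

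**Step 1: the count each half-width implies.**

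| Quantity | Calculation | Implied n | Range of n that rounds to the printed half-width |
|---|---|---|---|
| Perometer sensitivity | 3.8416 × 0.1275 / 0.036² | 378 | 368 to 388 |
| BEA sensitivity | 3.8416 × 0.0736 / 0.025² | 452 | 435 to 471 |
| Perometer specificity | 3.8416 × 0.2475 / 0.041² | 566 | 553 to 579 |
| BEA specificity | 3.8416 × 0.2304 / 0.039² | 582 | 568 to 597 |

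The specificity ranges overlap: any n from 568 to 579 gives both printed half-widths. The sensitivity ranges do not meet. They stay apart if the percentages are also allowed to be rounded (about 357 to 399 against 410 to 498). At the stated percentages they stay apart under Wilson, Agresti-Coull, Jeffreys and exact intervals, and with z = 2.

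**Step 2: which figure is out of line.** About 378 cases and 570 non-cases reproduce three of the four half-widths (3.6, 4.1, 3.9). The same 378 cases give 1.96 × √(0.0736/378) = 2.7 for BEA sensitivity, not 2.5.

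**Step 3: half-widths at the protocol's own counts.**

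| Cases | Perometer 85% | BEA 92% | Perometer upper limit | BEA lower limit | Gap |
|---|---|---|---|---|---|
| As printed | ±3.6 | ±2.5 | 88.6 | 89.5 | 0.9 |
| 378 | ±3.60 | ±2.73 | 88.60 | 89.27 | 0.7 |
| 352 | ±3.73 | ±2.83 | 88.73 | 89.17 | 0.4 |
| 350 | ±3.74 | ±2.84 | 88.74 | 89.16 | 0.4 |

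For specificity at 650 non-cases the half-widths are ±3.82 and ±3.69. The limits are then 58.8 and 60.3, a gap of 1.5 points against the printed 1.0 (59.1 against 60.1).

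**Step 4: the exact method.** Section 5 says exact binomial intervals were used, and its interval for 333/350 (92.34 to 97.15) reproduces. By that method at 350 cases, 92% (322/350) has a lower limit of 88.65%. For 85%, which is 297.5 cases, the upper limit is 88.45% with 297/350 and 88.70% with 298/350. The gap is then close to zero, and its sign turns on one patient.

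**The case against.** **Nothing depends on it.** By the normal approximation the intervals remain separate at 350 and at 378 cases. Even treating the two sensitivities as independent, 0.07/√((0.1275 + 0.0736)/350) gives z of about 2.9. This stands, and it is why the point is minor.

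**The perometer figure is described as reported, so it may come from other data.** This could explain two denominators. It does not rescue ±2.5, which is a projection for this study and by itself needs at least 435 cases.

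**Other incidence figures in the protocol reach 440 cases.** The introduction cites 40% lymphoedema by 18 months in an earlier trial; 40% of 1100 is 440, which gives ±2.53 for BEA. But this allows no drop-out, although section 2.0 plans for 10%, and it departs from the 35% used in Analysis 2. It would also make the perometer half-width ±3.3 rather than ±3.6. After 10% drop-out, 40% of 990 is 396, which gives ±2.67.

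**350 and 650 are one choice of base.** This is fair. Analysis 2 treats 1000 women as a minimum, and it compares the devices at the same visit, whereas the 85% in section 2.0 seems to concern early perometry predicting the 18-month outcome. Still, 350 is the protocol's stated 18-month expectation and 352 is the denominator in section 2.0 itself. Both give ±2.8.

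**The specificity figures are not wrong.** Agreed. The pair is consistent after rounding and conservative against 650. It belongs here only because all four figures should share one stated cohort.

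**Conclusion.** The concern holds. No single number of cases gives both ±3.6 at 85% and ±2.5 at 92%. The mismatch alone does not show which is wrong, but two facts point to the BEA figure: the other three half-widths fit one cohort, and the protocol's 350 to 352 cases give ±2.8. The printed half-width is too narrow by about 0.2 points (at 378 cases) to 0.3 points (at 350).

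The consequence is slight. By the normal approximation the 7-point claim survives, with a gap of about 0.4 points instead of 0.9. By the exact method that section 5 names, there is practically no gap at 350 cases. The conclusion assumes a common denominator for the two devices and 35% incidence among 1000 women followed to 18 months. ±2.5 would need at least 435 cases, or 43.5% of 1000.

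**What to change.** In section 2.0, state the number of cases and non-cases behind the intervals and recompute all four half-widths from it. With the Analysis 2 base of 350 and 650, by the normal approximation:

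- perometer sensitivity 85 ±3.7 (81.3 to 88.7)
- BEA sensitivity 92 ±2.8 (89.2 to 94.8)
- perometer specificity 55 ±3.8 (51.2 to 58.8)
- BEA specificity 64 ±3.7 (60.3 to 67.7)

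Name the interval method as well, since section 5 uses exact limits and the section 2.0 intervals are symmetric. If the perometer interval does come from earlier data, say so and give its denominator.

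The cost is a few corrected figures and a slightly less favourable sensitivity statement. Recruitment, visits and analyses are unchanged.

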Analysis 1

Sensitivity and specificity analysis of the BEA assessment (lymphoedema or not) against the 'gold standard' perometer assessment (lymphoedema or not) using data available by 6 months.

Analysis 2

Analysis of the sensitivity and specificity of the 18 month BEA assessment status (lymphoedema or not) against the 'gold standard' 18 month perometer assessment status (lymphoedema or not) using all data available at 18 months.

Analysis 3

Assessment of the relationship between perometer measurement and BEA measurement.

Analysis 4

Cox regression multivariate analysis of the time to Lymphoedema (as defined by perometer) to find out which combination of variables gives the best prediction of this complication.

Analysis details:

Analysis 1: Sensitivity and specificity analysis of the BEA assessment (lymphoedema or not) against the 'gold standard' perometer assessment (lymphoedema or not) using data available by 6 months. Can BEA be used instead of perometer in predicting lymphoedema status?

All cases with a 6 month BEA and perometer measurement will be used. This is acceptable even if some cases are treated as what we are asking is do cases measured at the same time (and therefore under the same circumstances whatever they are) agree in their assessment of lymphoedema status.

The two methods will not agree on their actual scores as perometer measurements are in percentage differences and BEA measures are ratios. However we will assess the relationship between all the pairs of values using statistical techniques recommended by Bland and Altman for assessing agreement between methods of measurements with multiple observations per individual^{36,311} (see also analysis 3).

With 1100 cases consented to having measurements taken and followed-up, we would expect 231 to have developed lymphoedema (positive) using perometer assessment and 869 to be negative at 6 months. If we accept that BEA status has at least 95% sensitivity and 95% specificity against the perometer status then the 95% CI for sensitivity based on 231 cases is 91.42% to 97.49% and for specificity based on 869 cases is 93.31% to 96.47% (CI's calculated by 'exact' method). Consequently if sensitivity is <91 % or specificity is <93% we can conclude that the true BEA rates are not as high as 95%. This analysis can be done 6 months after the last case has their 6 months measurements taken. The perometer is deemed to be the gold standard.

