All percentages for the 3 groups (A-C) are estimated from ALMANAC Trial data (see Annex 4d). None of the analyses outlined will use cases where a treatment for lymphoedema has been given prior to 6 months as explained above. A "treatment paradox" will not affect analyses 1 to 3 and treatment will be a variable in analysis. Potentially, the predictive value of a measurement at 6 months by perometry of the arm may be altered by treatment when assessing lymphoedema at 18 or 36 months. We do not believe this will occur for the majority of patients but in any case we will take account of this in the Cox multivariate regression analysis based on perometer measurements at 18 and 36 months and by looking at variables which include treatment with a compression sleeve. As we indicated in the flow diagram of this study, 3 possibilities may arise:

- Group A: Women in whom the arm volume increase is less than 4% at all time points up to 6 months (approximately 33% of the population; 330 individuals). None of these patients will undergo treatment within the first 6 months and therefore the measurement at 6 months will not be subject to "treatment paradox" and should they subsequently develop lymphoedema before 18 months, they will be registered as having developed the lymphoedema event in a time-dependant manner for the multivariate analysis and subsequent treatment will not affect this analysis.
- Group B: Women who will have developed a 4-10% arm volume increase by 6 months (estimated as 46% of the total group; 460 patients). Around 135 women from this group (with a 4-8.9% volume increase) will go into the PLACE trial and have a sleeve applied and a similar number will go into the PLACE trial and will not have an arm sleeve applied.

Thus, in this group there will be 325 patients (460 minus 135) who are not treated until they develop lymphoedema and will not have a "treatment paradox" for the same reason as previously described. Out of the 135 cases allocated to the sleeve arm within the PLACE trial, who are chosen at random, we will use their data in a multivariate analysis as we will incorporate it as a factor, sleeve versus no sleeve in building the model.

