- Group C: Women who develop greater than 10% arm swelling by 6 months (approximately 210 patients). Arm swelling of greater than 10% at 1 month will need confirmation but in current practice, we would review these patients at 3 months, before deciding to put on an arm sleeve as some women do observe amelioration of swelling over this period following the operation. Thus we will have 3 month perometer readings on all patients in this group to compare with 3 month BEA measurements. All other patients will provide 6 month perometer and BEA measurements and will therefore be eligible for the analysis of the prediction of arm swelling at 18 and 36 months. The data for patients who have undergone treatment before 6 months in this group will not be included in our multivariate analysis, although we expect few cases to be excluded in this way.

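### The perometer result chooses the visit at which BEA is scored, so BEA sensitivity and specificity describe no fixed visit, and three other statements in Section 5 do not fit that rule

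*Protocol*

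**What the plan says.** Section 2.0 sets a visit rule. For women who exceed 10% at 3 months, "sleeves will be applied and the 3 month BEA value compared to the perometer used in the analysis". It continues: "For all others, the 6 month value will be used".

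Section 5 makes three further statements about which data are used:

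- Analysis 1, details: "All cases with a 6 month BEA and perometer measurement will be used". The text accepts this even where some women have been treated.
- Opening of the discussion of Groups A to C: "None of the analyses outlined will use cases where a treatment for lymphoedema has been given prior to 6 months".
- Group C, defined as women above 10% by 6 months: "Thus we will have 3 month perometer readings on all patients in this group to compare with 3 month BEA measurements". All other patients are then said to supply 6-month pairs.

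Analysis 1 plans on 231 perometer positives and 869 negatives out of 1100, and on BEA having "at least 95% sensitivity and 95% specificity against the perometer status". Its reading rule is "if sensitivity is <91 % or specificity is <93% we can conclude" that the true BEA rates fall short of 95%.

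**The concern.** Under the Section 2.0 rule, a perometer reading above 10% at 3 months fixes the 3-month pair. A reading of 10% or less gives the perometer another chance at 6 months. BEA has no matching chance: a 3-month pair that is BEA-positive and perometer-negative is never scored. The positive column mixes two kinds of women, those already positive at 3 months (scored then) and those newly positive at 6 months. The negative column loses women who were positive at 3 months but below the line at 6.

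The result estimates accuracy at no visit a clinic could name. It is also unclear which table the 91% and 93% lines apply to, since Section 5 describes different sets of women. Settling only who is included would leave the outcome-dependent choice of visit in place.

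**Working it through.** **1. The Protocol's own figure.** Exact (Clopper-Pearson) 95% intervals for sensitivity on 231 positives:

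- 219/231: 91.10 to 97.29
- 220/231: 91.64 to 97.60
- 0.95 × 231 = 219.45: 91.34 to 97.43

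The printed 91.42 to 97.49 lies between the two whole-number results and within 0.1 point of the fractional one. The 18-month intervals reproduce exactly (333/350: 92.34 to 97.15; 618/650: 93.12 to 96.61). The interval arithmetic is not the problem.

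**2. What the rule estimates.** Let w be the share of rule-positives already perometer-positive at 3 months, Se3 the 3-month sensitivity, and Se6new the 6-month sensitivity among women negative at 3 and positive at 6 months. Then

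Se(rule) = w × Se3 + (1 − w) × Se6new.

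If sensitivity is 95% in every such group, the rule returns 95% and nothing is lost. Otherwise it can move either way. Take 231 positives, 100 of them positive at 3 months:

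- Se3 95%, Se6new 90%: (100 × 0.95 + 131 × 0.90)/231 = 92.2%, below Se3.
- Se3 90%, Se6new 95%: (100 × 0.90 + 131 × 0.95)/231 = 92.8%, above Se3.

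**3. Size under stated assumptions.** From the Protocol: mean increases of 4.0% and 5.14% at 3 and 6 months and a perometer SD of 1.2% (Section 7), r = 0.92 with BEA (Sections 1.4 and 7), and 21% above 10% by 6 months (Section 2.0). Assumed: normally distributed swelling; 3-to-6-month correlation of true swelling 0.5, 0.7 or 0.9; 6-month SD 1.0 or 1.25 times the 3-month SD; 30% of BEA error variance persisting across visits; one reading per visit; BEA cut-off set to give 95% sensitivity at an untreated 6-month visit. A sleeve effect of 0, 2 or 4.1 points was applied from 3 months. The 4.1 comes from the observational study in Section 1.4, which is a different setting.

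Sensitivity, %:

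| Correlation | SD ratio | Fixed 3 m | Fixed 6 m, untreated | Fixed 6 m, sleeve effect 4.1 | Section 2.0 rule |
|---|---|---|---|---|---|
| 0.5 | 1.00 | 94.35 | 95.00 | 94.26 | 94.33 |
| 0.7 | 1.00 | 94.30 | 95.00 | 93.60 | 93.93 |
| 0.9 | 1.00 | 94.47 | 95.00 | 92.23 | 93.24 |
| 0.5 | 1.25 | 91.67 | 95.00 | 94.51 | 93.51 |
| 0.7 | 1.25 | 91.90 | 95.00 | 94.06 | 93.11 |
| 0.9 | 1.25 | 92.13 | 95.00 | 93.22 | 92.35 |

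Check of row 3: 12.98% are positive at 3 months, so w = 12.98/21 = 0.618. Se6new is 91.24, and 0.618 × 94.47 + 0.382 × 91.24 = 93.24.

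- Against the untreated 6-month value, the rule is lower in all six rows, by 0.7 to 2.7 points.
- Against the 6-month value with the 4.1-point sleeve effect, the rule is higher by 0.1 to 1.0 point at equal spread and lower at the wider 6-month spread.
- Against the 3-month value, the rule is lower at equal spread (0.02 to 1.2 points) and higher at the wider spread (0.2 to 1.8 points).
- Over all 18 combinations of correlation, spread and sleeve effect, the rule falls below both fixed visits in 6.

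Specificity under the rule exceeds the fixed 6-month value in all 18, by 0.1 to 2.7 points. The cut-off that gives 95% sensitivity gives a 6-month specificity of only about 81% to 85% in this model, so the specificity shift should be read for direction only.

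If BEA is instead put on the same scale with a common 10% cut-off, the sensitivity loss against the untreated 6-month table is larger, 2.1 to 8.7 points.

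**4. Bearing on the 91% line.** Below 91% means at most 210 of 231. The binomial chance of that is 0.6% if sensitivity is 95%, 10.8% at 93.2%, and 24.5% at 92.3%, which is about the lowest value the rule produced.

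**5. The statements side by side.** A woman above 10% at 3 months and sleeved before 6 months is scored at 3 months under Section 2.0, at 6 months under the Analysis 1 details, and not at all under the exclusion sentence. These cannot all apply to one table.

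**The case against.** The strongest reply is that the 91% and 93% lines belong to Analysis 1, whose details already describe a fixed 6-month table, so the Section 2.0 rule may never reach them. That is a fair reading, and it is why the fix below keeps that table. It does not dispose of the point: Analysis 1 is titled as using data available by 6 months, Section 2.0 states its rule for the analysis without limit, and the exclusion sentence contradicts the Analysis 1 details directly.

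A reader might infer that the rule pushes sensitivity below its value at either fixed visit. The documents do not support that. It needs a similar spread at both visits and little sleeve effect, and the second is an odd assumption for a rule that exists because sleeves are applied. A reader might also infer that the rule alone decides whether BEA fails the 91% line. With BEA calibrated to 95%, the rule gives about 92% to 94%, still above 91%. With a common 10% cut-off, fixed-visit sensitivity is already far below 91%, so the rule changes no conclusion there.

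The simulation classifies on one reading per visit, while Sections 1.4 and 7 define lymphoedema as above 10% on at least two occasions. That overstates how far positives are selected on upward perometer error.

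On Group C, a literal reading would score a woman who first exceeds 10% at 6 months on her perometer-negative 3-month pair. But the sentence follows a remark about reviewing 1-month swelling at 3 months and may only say that the readings will exist. The wording is ambiguous, and no loss of positives can be computed from it.

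**Conclusion.** The point holds as a defect of definition. The Section 2.0 rule makes the choice of visit depend on the reference result, so the estimates belong to no fixed visit, and it cannot be reconciled with the Analysis 1 details or with the exclusion of women treated before 6 months. Against an untreated 6-month table, sensitivity is about 1 to 3 points lower when BEA is calibrated to 95% there, more with a common 10% cut-off, and specificity is somewhat higher. Those sizes rest on the assumed between-visit correlation, spread and error structure. Against a 3-month table, or a 6-month table that includes sleeved women, the direction is undetermined, because the Protocol gives neither the sleeve effect, the spread at each visit nor the between-visit correlation for this population. The shift can change the odds of crossing the 91% line but does not settle that result.

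**What to change.** Reconcile Section 2.0 and the three Section 5 statements to one prespecified visit rule that does not depend on the perometer result:

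- Apply the 91% and 93% lines to the 6-month pair for all women measured at 6 months, as the Analysis 1 details already state.
- Flag women sleeved before 6 months and show that table with and without them. Reword the exclusion sentence to match.
- Report the 3-month pair for all women measured at 3 months as a separate table.
- Reword the Group C text so that a woman who first exceeds 10% at 6 months has one defined place in each table.

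The cost is analysis wording and one extra two-by-two table, since both pairs are already on the visit schedule. The 6-month table will either contain some sleeved women or have fewer positives, and showing both versions makes that visible. The rule for starting a sleeve is not touched.
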